6.3 Rules for Missing Data

Missing data will not be imputed, except for missing date information for AEs and concomitant medications. The imputed dates will be used to determine the treatment-emergent period. For AEs with a partial date, available date parts (year, month, and day) of the partial date will be compared with the corresponding date components of the start date and end date of the treatment-emergent period to determine if the event is treatment emergent. When in doubt, the AE will be considered treatment emergent by default. The following rules will be applied to impute partial dates for AEs:

- If start date of an AE is completely or partially missing, impute as follows:
 - If both month and day are missing and year = year of first dose date, then set to first dose date.
 - If both month and day are missing and year i- year of first dose date, then set to January 1.
 - If day is missing and month and year = month and year of first dose date, then set to first dose date.
 - If day is missing and month and year i- month and year of first dose date, then set to first of the month.
 - If start date is completely missing and AE end date is on or after the first dose date, set to first dose date.
 - If start date is completely missing and AE end date is prior to the first dose date, do not impute an AE start date.
- If end date of an AE is partially missing, impute as follows:
 - If both month and day are missing, then set to December 31.
 - If only day is missing, then set to last day of the month.
 - If end date is completely missing, do not impute.

When the start date or end date of a medication is partially missing, the date will be imputed to determine whether the medication is prior or concomitant (or both). The following rules will be applied to impute partial dates for medications:

- If start date of a medication is partially missing, impute as follows:
 - If both month and day are missing, then set to January 1.

- If only day is missing, then set to the first of the month.
- If end date of a medication is partially missing, impute as follows:
 - If both month and day are missing, then set to December 31.
 - If only day is missing, then set to last day of the month.
- If start date or end date of a medication is completely missing, do not impute.

Listings will show the original date information without imputation, but derived parameters (TEAE indicator and duration of AE) will be flagged to indicate the type of imputation performed.

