6.0 DEFINITIONS, COMPUTATIONS, AND CONVENTIONS

6.1 Definitions and Computations

Study Day

Study day will be calculated in reference to the date of first injection (Day 1). For visits conducted on or after the first injection date, study day is calculated as (visit date – first injection date + 1). For visits conducted before the first injection date, study day is calculated as (visit date – first injection date). There will be no Day 0.

Date of First Injection and Date of Last Injection of Study Vaccine

The date of the first injection of study vaccine is defined as the date a subject receives the first injection of the study vaccine. The date of the last injection of study vaccine is the date a subject receives the last injection of the study vaccine.

Treatment-Emergent Period

The reporting period for all non-serious AEs begins at the time of the first study injection (Day 1) through EOS Visit. All AEs will be captured on the AE eCRF.

Any SAE that occurs from the time the consent is signed through EOS Visit, whether or not the SAE is related to the study treatment, must be reported.

The treatment-emergent (TE) period is defined as time from the first study injection through EOS Visit.

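### SAP 6.3 moves a partly dated AE start to the first dose date without checking the end date, so an SAE that ended during screening can be counted as treatment-emergent

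*SAP*

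**What the plan says.** SAP 6.3 gives two rules that move a partial AE start date to the first dose date. With only the year known: "If both month and day are missing and year = year of first dose date, then set to first dose date". With month and year known: "If day is missing and month and year = month and year of first dose date, then set to first dose date". Neither refers to the end date of the event.

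The end date is consulted only when nothing is known of the start: "If start date is completely missing and AE end date is prior to the first dose date, do not impute an AE start date". If such an event ended on or after the first dose, its start is set to the first dose date.

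The imputed dates matter for classification: "The imputed dates will be used to determine the treatment-emergent period". The same section has the programmer compare the available parts of the partial date with the treatment-emergent period, and adds: "When in doubt, the AE will be considered treatment emergent by default".

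On collection, SAP 6.1 requires reporting of "Any SAE that occurs from the time the consent is signed through EOS Visit", and Protocol 10.9.2 puts every SAE on the AE case report form. SAP 6.1 starts the treatment-emergent period at the first injection. SAP 8.7 defines a TEAE by onset or worsening in that period and plans a table of treatment-emergent SAEs.

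For partial AE end dates, SAP 6.3 says "If both month and day are missing, then set to December 31" and "If only day is missing, then set to last day of the month". It states no upper bound.

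**The concern.** The plan recognises that an event which ended before dosing cannot have begun at dosing, but it applies that reasoning only where the start date is completely unknown. With more information about the start, it stops using the end date and assigns a start that the end date rules out.

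What is at stake is the treatment-emergent SAE count and the other TEAE outputs that the same event enters. Safety is purely descriptive here (SAP 8.0 and 8.7), so the counts are the result. A screening event shown as following vaccination would have to be explained case by case.

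**Working it through.** The documents state no figure on this point, so there is none to reproduce. The check applies the SAP 6.3 rules literally to example dates.

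**Inputs**
- From the documents: the rules above; screening of up to 4 weeks (SAP 2.0) with one possible 7-day extension (Protocol 9.1.2); follow-up to Day 393; about 20 + 70 = 90 subjects per pooled arm (SAP 4.0).
- Assumed: first dose 17 Oct 2022; a screening SAE that ended 5 Oct 2022; duration = end − start + 1. The SAP lists duration as a derived parameter but gives no formula.

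**Same event, four ways of recording its start**

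| Start recorded as | Imputed start | Status read literally | Duration (days) |
|---|---|---|---|
| 2022 | 17 Oct 2022 | treatment-emergent | 5 − 17 + 1 = −11 |
| Oct 2022 | 17 Oct 2022 | treatment-emergent | 5 − 17 + 1 = −11 |
| Sep 2022 | 1 Sep 2022 | not treatment-emergent | 30 + 5 = 35 |
| completely missing | none | no start date in the period | not defined |

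The first two rows place the start 17 − 5 = 12 days after the end.

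**Range.** For an event that ended k days before the first dose, the derived duration is 1 − k. For k = 1 to 28 this runs from 0 to −27. With the extension (k = 35) it reaches −34.

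**Reach of each rule.** Assume first doses spread evenly over a 365-day year and take every day of a 28-day screening window: 365 × 28 = 10,220 combinations. At each month boundary, 1 + 2 + … + 28 = 406 of them fall in the previous month.
- Same year as first dose: 1 − 406/10,220 = 96%.
- Same month as first dose: 1 − (12 × 406)/10,220 = 52%.

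So if a screening SAE has a start known only to the year, the first rule nearly always applies. If it is known to the month, the second applies about half the time. These are not probabilities of a misclassified event: the documents give neither a rate of screening SAEs nor a rate of partial dates.

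**Size of one event.** 1/90 = 1.1% of a pooled arm, or 1/20 = 5% of a Part 1 group.

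**End dates.** With the same first dose, Day 393 is 13 Nov 2023. An AE starting 1 Nov 2023 with its end recorded as 2023 is given 31 Dec 2023, which is 48 days past Day 393. With its end recorded as Nov 2023 it is given 30 Nov 2023, 17 days past. Over all first-dose dates in a year, the overrun is 0 to 365 days when only the end-of-study year is known and 0 to 30 days when the month is known.

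**The case against.** The strongest reply is that the case is very narrow. Non-serious AEs are collected only from the first injection, and Protocol 10.1 keeps conditions present before it off the AE form. That leaves SAEs between consent and dosing, in subjects who were still dosed, with a partial start date but an end date known to precede dosing. SAEs are reported within 24 hours with a narrative (Protocol 10.9.2), and data are queried before lock (Protocol 13.6). All of this stands, and it makes the event rare. It does not make it impossible, because the SAE instructions in SAP 6.1 and Protocol 10.9.2 specifically bring post-consent SAEs into the AE data.

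A second reply is that an event known to have ended before dosing is not in doubt, so the default does not apply, and that the SAP 8.7 definition requires onset or worsening in the period. A careful programmer could rely on that. But SAP 6.3 explicitly gives the event a start inside the period and says that imputed dates decide. The definition does not cancel that instruction, so the text at best pulls two ways.

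Third, listings show the original dates and flag an imputed TEAE indicator or duration. This makes an error traceable there, but does not correct the table count.

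A reader might also infer that the unbounded end dates distort the safety results. The documents do not support that. Treatment emergence depends on onset or worsening, and no AE table listed in SAP 8.7 summarises duration. Related SAEs may be followed beyond the end-of-study visit (Protocol 9.4.5.1 and 10.10.2), so a late end date is not wrong in itself.

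**Conclusion.** The point holds as a minor inconsistency in a stated rule. Followed literally, SAP 6.3 can give an SAE that ended before the first injection a start after its own end and so place it among the treatment-emergent SAEs. The result is certain once such a record exists, but the record should be rare. It would shift an arm's SAE percentage by about 1.1 points per event. The negative durations rest on an assumed formula; the reversed order of start and end does not.

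Two stronger inferences are not supported. One is that the safety comparison is biased: the rules are the same for every group, no safety hypothesis is tested, and only pre-dose SAEs are exposed. The other is that the SAP already classifies the completely missing start correctly: it says only that no start is imputed, so the classification is an inference. No immunogenicity endpoint is affected.

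**What to change.** In SAP 6.3, apply the two rules that set the start to the first dose date only if the AE end date is missing, or if its latest possible value given the known date parts is on or after the first dose date. Otherwise, set the start to the later of the consent date and the first day of the known month or year, and class the event as not treatment-emergent. In the example, a start recorded as Oct 2022 with consent on or before 1 Oct would become 1 Oct 2022, a duration of 5 − 1 + 1 = 5 days, outside the treatment-emergent period.

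The cost is a line or two of SAP text and one condition in the program, best added before database lock. The SAP should also state that a partial end date is resolved to its latest value before the start rule is applied.

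Optional, and of minor value because no planned table uses it: bound imputed AE end dates at last contact or death. The end-of-study visit should not be the bound for related SAEs followed beyond it, since that could cut off a true resolution date. This option needs a last-contact date to be derived for each subject.

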7.0 TIMING OF ANALYSES

The administration method of vaccine utilized in Part 2 of the study will be selected by Dynavax in consultation with the Department of Defense (DoD) after Day 57 immunogenicity data in Part 1 subjects become available. The evaluation will be based on unblinded data. Blinding will be retained for those who are blinded per study requirements throughout the study.

Final analyses will be carried out after the last participant has completed their last study visit, the study database has been authorized by Dynavax as complete and final, and major protocol deviations have been identified.

8.0 STATISTICAL METHODS

This is a phase 2, randomized, active-controlled, observer-blinded, multicenter trial of the immunogenicity, safety, and tolerability of rF1V vaccine with CpG 1018 compared with rF1V vaccine alone in adults.

Part 1 objectives will be evaluated descriptively. The administration method of vaccine utilized in Part 2 of the study will be selected by Dynavax in consultation with the Department of Defense (DoD) after Day 57 immunogenicity data become available to determine whether the GMC 1 month after 2 doses of rF1V vaccine with CpG 1018 using the selected administration method is at least 2 times higher than that 4 weeks after 2 doses of rF1V vaccine in Group 3.

The proposed statistical planning for Part 2 is presented according to the objectives. Data from Part 1 and Part 2 will be combined to evaluate the Part 2 objectives. No multiplicity adjustments are made, and all statistical tests will be conducted at 5% two-sided Type I level unless otherwise specified. All confidence intervals are two-sided 95% confidence intervals unless otherwise specified.

All analyses of demographics and baseline characteristics, medical history, vaccine exposure and safety will be summarized in a descriptive manner. In general, continuous variables will

be summarized by number of subjects, mean, standard deviation, median, quartiles, minimum and maximum, and categorical variables will be summarized by number and percentage of subjects in each study group as appropriate. All data processing, summarization, and analyses will be performed using SAS Version 9.4 or higher. Specifications for tables, graphs, and data listings will be provided in the tables, figures, listings (TFL) specifications document as needed. No specific safety hypotheses will be tested.

8.1 Subject Disposition

Subject disposition will be summarized for all enrolled subjects including subjects in the safety, PP and mITT populations and subjects discontinuing the study along with the reasons for discontinuation (as documented on the case report form Study Completion).

A listing of subjects discontinuing the study after enrollment will be produced.

8.2 Protocol Deviations

For the purpose of selecting subjects for the per-protocol population, a major protocol deviation is defined as one of the following:

- not meeting one or more enrollment criteria,
- vaccine was not given per-protocol,
- [REDACTED] serum sample obtained outside protocol specified visit window 4 weeks following the second study injection for rF1V vaccine with CpG 1018 groups ([REDACTED]) and the third study injection for rF1V vaccine only group ([REDACTED]).

This deviation will be identified at both visits, but will be applied for each group by corresponding visit for exclusion purpose post database lock (DBL), as this deviation is dependent upon treatment assignment for complete adjudication, e.g. a subject who was vaccinated per protocol but who had the Day [REDACTED] blood sample drawn out of window, is marked as a major protocol deviation. Following DBL and unblinding, if the subject is found to be in the rF1V vaccine with CpG-1018 group, although the out of window of the sample is considered a major protocol deviation, the subject will be included in the per protocol analysis set provided no other major protocol deviations apply.

- received prohibited concomitant medications.

The following non-study medications are prohibited for the purpose of evaluating per-protocol population:

- Any licensed COVID-19 vaccine or inactivated vaccine (including vaccines containing mRNA or CpG)
 - :S 14 days prior to each study injection through 14 days after each study injection
- Any live vaccine
 - :S 28 days prior to each study injection through 28 days after each study injection
- Other concomitant medications

- :S 28 days prior to vaccine injection (Day 1) through 28 days after the third study vaccine injection [REDACTED]
 - Systemic corticosteroids (more than 3 consecutive days) or other immunomodulators or immunomodulators immune suppressive medication, with the exception of inhaled steroids
 - Any other investigational medicinal agent
- :S 90 days prior to vaccine injection (Day 1) and through 28 days after the third study vaccine injection [REDACTED]
 - Granulocyte or granulocyte-macrophage colony-stimulating factor
 - Immunoglobulins or any blood products
 - Antisense oligonucleotides
 - Drugs/ investigational agents with very long half-lives (defined as 2: 60 days)
- At any time prior to vaccine injection (Day 1) and through 28 days after the third study vaccine injection [REDACTED]
 - DNA plasmids or other genetic therapy intended to integrate permanently into host cells

A listing of subjects with major protocol deviations will be provided describing their deviations. Any exclusions from analysis populations due to protocol deviations and other reasons will also be listed.

8.3 Demographics and Baseline Characteristics

Demographic and baseline characteristics will be listed by subject and summarized using the Safety Population. Descriptive summary statistics (sample size, mean, median, SD, and range, when appropriate) will be provided for the continuous variables such as age, weight, and height. Count and percentage will be reported for categorical variables such as sex, race, and ethnicity.

Listings will be provided for these parameters for all subjects.

8.4 Prior and Concomitant Medications

Prior and concomitant medications will be coded using the World Health Organization (WHO) Drug Dictionary. Prior medications are drugs and therapies used before the first dose date. Medications or therapies are considered concomitant if exposure occurs after the first dose date. The number and percentage of subjects with concomitant medications will be presented alphabetically by anatomical therapeutic chemical (ATC) class and by decreasing order of frequency of preferred terms within each ATC class for the safety population. Subjects taking the same medication multiple times will be counted once per medication.

All medications recorded on the case report form will be listed.

8.5 Medical History

Medical history will be coded using the Medical Dictionary for Regulatory Activities. Medical history will be summarized by System of Organ Class (SOC) and Preferred Term (PT) for safety population. All medical history data will be provided in a listing.

8.6 Immunogenicity Analyses

The primary and other immunogenicity endpoints will be analyzed using the mITT population. Sensitivity analyses on immunogenicity data will also be presented using the PP population.

Immunogenicity will be measured by serum rF1V [REDACTED] concentration at each visit.

Data from Part 1 subjects and Part 2 subjects will be combined to evaluate the Part 2 objectives. No multiplicity adjustment is proposed.

Additional analyses may be attempted, including analysis to quantify antibody decay over time.

Part 1 Primary Objective: To select one of the two methods of administration of rF1V vaccine with CpG 1018 for Part 2 by comparing humoral immunization response 28 days after the second dose of vaccine

Endpoint: Ratio of geometric mean ELISA concentrations (GMCs) between rF1V vaccine with CpG 1018 and rF1V vaccine.

Estimand: GMCs and associated two-sided 95% confidence intervals for each of the 3 study groups will be computed by exponentiating the mean and associated Student's t confidence interval of the log10 transformed individual antibody concentrations assuming Normal distribution. The ratio of GMCs and associated two-sided 95% confidence interval will be compared between rF1V vaccine with CpG 1018 and rF1V vaccine, using Student's t method. The ratio of GMCs and associated two-sided 95% confidence interval between two administration methods of rF1V vaccine with CpG 1018 vaccines will also be produced.

Criterion for evaluation: GMC 1 month after 2 doses of rF1V vaccine with CpG 1018 using the selected administration method is at least 2 times higher than that 4 weeks after 2 doses of rF1V vaccine.

Part 2 Primary Objective 1: To assess the utility of a 2-dose schedule of rF1V vaccine with CpG 1018 as measured by reduction in time to onset of predicted rF1V protection

Endpoint: Predicted protection (percentage of subjects reaching the [REDACTED] threshold that corresponds to 50% predicted vaccine efficacy) at Week [REDACTED] after 2 doses of rF1V vaccine with CpG 1018 as that at Week [REDACTED] after 3 doses of rF1V vaccine without CpG 1018. The [REDACTED] threshold that corresponds to 50% predicted vaccine efficacy will be obtained from a model using [REDACTED] data after 3 doses of rF1V vaccine (or after 2 doses of rF1V

with CpG 1018 TBD) in this study. The threshold and the model used will be described in a separate report. Part 2 Primary Objective 1 can only be evaluated after the determination of this threshold.

Estimand: Percentage of subjects reaching the [REDACTED] threshold and associated 95% two-sided Clopper-Pearson confidence intervals will be computed. Fisher's exact tests will be used to compare predicted protection rate between study groups.

Criterion for evaluation: Similar percentage of subjects reaching the [REDACTED] threshold that corresponds to 50% predicted vaccine efficacy after 2 doses of rF1V vaccine with CpG 1018 as compared to that after 3 doses of rF1V vaccine.

Part 2 Primary Objective 2: To assess the serum [REDACTED] concentration to rF1V vaccine with CpG 1018 compared with rF1V vaccine 28 days after the second dose of vaccine

Endpoint: Ratio of geometric mean ELISA concentration (GMC) between rF1V vaccine with CpG 1018 and rF1V vaccine at Week [REDACTED].

Estimand: GMCs and associated two-sided 95% confidence intervals will be computed by exponentiating the mean and associated Student's t confidence interval of the log10 transformed individual antibody concentrations assuming Normal distribution. The ratio of GMCs and associated two-sided 95% confidence interval will be compared between rF1V vaccine with CpG 1018 and rF1V vaccine, using ANOVA if site can be used as an adjustment factor in the model or Student's t method.

Criterion for evaluation: 2-times increase in [REDACTED] GMC point estimate after the second dose of rF1V vaccine with CpG 1018 to that after the second dose of rF1V vaccine.

Part 2 Secondary Objective: To assess the serum [REDACTED] concentration to rF1V with CpG 1018 at selected time points after each dose

Endpoint: GMC and seroconversion rate of serum rF1V [REDACTED] titers at the following selected time points after each dose of vaccine:

- [REDACTED]

- [REDACTED]

[figure not shown]
Seroconversion is defined as the presence of detectable antibody in subjects who had no detectable antibody levels at Day 1, or a 2: 2-fold increase in antibody level in subjects who had detectable antibody levels at Day 1.

Estimand: GMCs and associated two-sided 95% confidence intervals will be computed by exponentiating the mean and associated Student's t confidence interval of the log10 transformed individual antibody concentrations assuming Normal distribution.

Seroconversion rate and associated 95% two-sided Clopper-Pearson confidence intervals will be computed.

Criteria for evaluation: GMC and seroconversion rate point estimates from rF1V vaccine with CpG 1018 to meet or exceed results from rF1V vaccine at relevant visits.

Part 2 Exploratory Objective 1: [REDACTED]

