4.3 Randomization and Blinding

This is an observer-blinded clinical study. Both the study subjects and the study personnel involved in safety assessment (observers) will be blinded to treatment assignments. Designated unblinded study-site personnel will be responsible for preparing and administering the study injection.

In Part 1, subjects will be randomized 1:1:1 to Group 1, 2, or 3. In Part 2, subjects will be randomized 1:1 to 1 of 2 groups (ie, either Group 1 and 3 or Group 2 and 3) as determined from Part 1. Randomization will be stratified by site.

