2.0 STUDY OVERVIEW

This is a phase 2, randomized, active-controlled, observer-blinded, multicenter trial of the immunogenicity, safety, and tolerability of rF1V vaccine with CpG 1018 compared with rF1V vaccine alone in adults. Approximately two hundred healthy adults 18 to 55 years of age will be enrolled to compare a two-dose regimen of rF1V with CpG 1018 administered on study Days [REDACTED] with a three-dose regimen of rF1V vaccine alone administered on [REDACTED].

The study will be conducted in 2 parts (Part 1 and Part 2). The table below outlines study drug administration in both parts. When investigational product is co-administered as 2 separate injections, the injections should be administered in close physical proximity to each other (within approximately 1 inch).

Injections will be administered by study personnel not otherwise involved in the subjects' safety evaluation. Recording and evaluation of safety information and laboratory data will be performed by observers blinded to the subjects' treatment assignment.

Part 1:

There will be 2 methods of rF1V vaccine with CpG 1018 administration:

- Group 1 (N = approximately 20): rF1V vaccine and CpG 1018 will be co-administered as 2 separate injections on Days 1 [REDACTED]
[REDACTED].
- Group 2 (N = approximately 20): bedside mix of rF1V vaccine + CpG 1018 (administered as 1 injection) and placebo will be administered as 2 separate injections on [REDACTED]

In addition, rFIV vaccine will be administered alone without CpG 1018:

- Group 3 (N=20): rF1V vaccine and placebo will be administered as 2 separate injections on Days [REDACTED]

All Groups will receive 2 injections at each treatment visit to maintain the blind.

Part 2: Part 2 will begin after immunogenicity assessments from the [REDACTED] visit in Part 1 are completed. The method of vaccine administration method that is selected from Part 1 will be evaluated in Part 2.

- Group 1 (if selected) (N=70): rF1V vaccine co-administered with CpG 1018
- Group 3 (N=70): rF1V vaccine co-administered with placebo

OR

- Group 2 (if selected) (N = 70): bedside mix of rF1V vaccine and CpG 1018
- Group 3 (N=70): rF1V vaccine

Subjects will be followed through Day 393 (Week 56)

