4.0 SAMPLE SIZE CONSIDERATIONS

Part 2 primary objective 1 is to assess the utility of a 2-dose schedule of rF1V vaccine with CpG 1018 as measured by reduction in time to onset of predicted rF1V protection. The predicted protection will be based on a [REDACTED] meter threshold. Previous animal studies have established protective efficacy in animals. Since a human efficacy study is not feasible, an immunobridge from animal data to human data via the [REDACTED] test will be used to predict the protective efficacy in humans using a regression model. An initial predicted protection threshold will be calculated based on the data generated in this study in Group 3 after 3 doses of rF1V vaccine. Once the threshold is identified, it will be applied to the study groups to evaluate the Part 2 objectives. In addition to the previous animal studies conducted to establish protective efficacy, a new animal model utilizing rF1V vaccine with CpG 1018 will be developed to establish the protective level of antibody for CpG 1018 containing vaccines. Additional analyses will include a predicted protection threshold that will be calculated based on the data generated under the new animal model after 2 doses of rF1V vaccine with CpG 1018. In both instances, the animal-to-human immunobridge and the identification of the predicted protection thresholds will be documented in a separate report.

A similar approach was used to analyze the previous Phase 2a (NCT00332956) and Phase 2b (NCT01122784) study data using the animal model from the previous animal studies. Thresholds that corresponded to 50% predicted protective efficacy in humans were established for those trials. In a pooled analysis of these previous immunobridge studies, 93% (95% Clopper Pearson confidence interval [CI] = 85%, 98%) of subjects reached the predicted protection threshold.

It is assumed that a similar percentage of the subjects in Group 3 will reach the threshold identified in this study. When this threshold is applied to both Part 2 study groups, a similar lower bound of the 95% CI is desired across the groups. Table 4-1 shows the lower bound of 95% Clopper Pearson CI for different observed levels of predicted protection assuming 85 of the 90 planned subjects (Part 1 N = 20 and Part 2 N =70) will have data available for the evaluation. Thus, with a predicted protection level of 93%, the lower bound of the 95% CI would be 85%.

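### Allocation is stratified by site, but the Part 1 GMC ratio ignores site, and for Part 2 primary objective 2 the SAP leaves open whether a site-adjusted or an unadjusted ratio is read against 2.

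*SAP*

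**What the plan says.** Protocol 4.3 gives the allocation: "In Part 1, subjects will be randomized 1:1:1 to Group 1, 2, or 3", then "In Part 2, subjects will be randomized 1:1 to 1 of 2 groups", and "Randomization will be stratified by site".

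SAP 8.6 gives the analyses of the GMC ratios.

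- **Part 1.** The ratio of GMCs and its 95% interval "will be compared between rF1V vaccine with CpG 1018 and rF1V vaccine, using Student's t method". The criterion is a GMC at least twice that of Group 3. SAP 8.0 says that Part 1 objectives are evaluated descriptively.
- **Part 2 primary objective 2.** Each group's GMC is the back-transformed raw mean of log10 concentration. The ratio and its interval are obtained "using ANOVA if site can be used as an adjustment factor in the model or Student's t method". The criterion is a doubling of the "GMC point estimate after the second dose of rF1V vaccine with CpG 1018 to that after the second dose of rF1V vaccine". Part 1 and Part 2 data are combined for this objective.

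Neither document gives a minimum number of subjects per site, a rule for pooling small sites, or an order of preference between the two methods.

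**The concern.** There are two separate issues.

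**Efficiency.** Stratified allocation balances the groups within sites and so removes most between-site variation from the group contrast. A two-sample t interval still carries that variation in its error term. If site matters, the interval is wider than the design requires. Part 1 has the smallest groups, about 20 each.

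**An open estimator for a primary criterion.** For objective 2 the raw GMC ratio and the ANOVA ratio are different numbers. The criterion is a bare point estimate against 2, with no interval bound or test to cushion a change of estimator. SAP 7.0 bases the Part 1 evaluation on unblinded data, and those subjects are pooled into objective 2. At stake is whether a primary criterion can be called met or not met according to a choice that the plan leaves undecided.

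**Working it through.** **Inputs from the documents.** Site-stratified allocation, 1:1:1 in Part 1 and 1:1 in Part 2 (Protocol 4.3). About 20 per group in Part 1 (SAP 2.0). For the pooled set, "85 of the 90 planned subjects (Part 1 N = 20 and Part 2 N =70) will have data available for the evaluation" (SAP 4.0), a loss of 5/90 = 5.6%. Two-sided 95% intervals (SAP 8.0).

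**Assumptions, because the documents give no figure.** Total log10 SD 0.5; 3 or 6 sites of unequal size; site share of variance from 0 to 0.30; permuted blocks of 6 (Part 1) and 4 (pooled set).

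**The plan's own figure.** The only precision table is SAP Table 4-1 (Clopper-Pearson, N = 85). It reproduces: 81/85 gives 88.4-98.7%, 79/85 gives 85.3-97.4% and 77/85 gives 82.3-95.9%. It concerns predicted protection. No precision is stated for a GMC ratio.

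**Step 1: unadjusted interval.** Half-width on the log10 scale = t × SD × √(2/n).

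- Part 1: 2.024 × 0.5 × √(2/20) = 0.320, so the interval runs from the ratio divided by 10^0.320 = 2.09 to the ratio times 2.09.
- Objective 2: 1.974 × 0.5 × √(2/85) = 0.151, a factor of 1.42.

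**Step 2: expected effect of adjusting for site.** Let site have share ρ of the variance and let there be K equal sites. The realised between-site part is about ρ(K−1)/K, so adjusted width / unadjusted width ≈ √[(1−ρ) / (1−ρ+ρ(K−1)/K)].

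- ρ = 0.10: √(0.90/0.967) = 0.965 with K = 3; √(0.90/0.983) = 0.957 with K = 6.
- ρ = 0.20: √(0.80/0.933) = 0.926 with K = 3; √(0.80/0.967) = 0.910 with K = 6.

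This ignores lost degrees of freedom and imperfect balance, which bring the ratio back towards 1, mainly in Part 1.

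**Step 3: simulation of both methods.** There were 1,500 runs per setting. Each data set was analysed by two-sample t and by ANOVA on group plus site, using the two groups being compared. Ranges cover 3 and 6 sites.

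| Site share | Width ratio, Part 1 | Width ratio, objective 2 | Objective 2: opposite sides of 2, true ratio 2.0 | Same, true ratio 2.5 |
|---|---|---|---|---|
| 0 | 1.00-1.02 | 1.00 | 0.9-1.7% | 0.7-0.9% |
| 0.05 | 0.99-1.00 | 0.98-0.99 | 2.1-2.2% | 0.4-0.8% |
| 0.10 | 0.97-0.98 | 0.96-0.97 | 2.1-3.5% | 1.1-1.5% |
| 0.20 | 0.93 | 0.92-0.94 | 2.9-3.8% | 0.9-1.7% |
| 0.30 | 0.87-0.90 | 0.86-0.89 | 3.7-4.6% | 0.7-2.1% |

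For shares of 10-20% the unadjusted interval is therefore wider by 1/0.98 = 1.02 to 1/0.92 = 1.09, that is 2-9%. The Monte Carlo standard error of a 2% rate is √(0.02 × 0.98/1500) = 0.4 percentage points, so small differences down the last two columns should not be read closely.

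**Step 4: how far apart the two objective 2 ratios are.** Over all settings the median factor between them is 1.003-1.017, and the 95th percentile is 1.011-1.057. At a 10% share the 95th percentile is 1.027-1.036. At the upper end, a ratio of 2.00 by one method then corresponds to between 2.00/1.036 = 1.93 and 2.00 × 1.036 = 2.07 by the other. The spread scales with the SD: for SD 0.3 to 0.7 the largest 95th-percentile factor is about 1.03-1.08.

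**Step 5: validity of the unadjusted interval.** Its coverage rises from about 95% with no site effect to about 96-97% at a 30% share. It is conservative, not wrong.

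**The case against.** The strongest counter-case has five parts.

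1. *Part 1 is not open.* Student's t is the only stated method, and Part 1 is descriptive. This stands. A reader might infer that the Part 1 selection ratio could also be either of two numbers; the SAP does not support that.
2. *Width decides nothing.* Both 2-fold criteria are stated on the GMC or its point estimate, without an interval bound. This stands. A reader might infer that the wider interval could change a verdict; under the stated criteria it cannot.
3. *A site effect is not shown.* The number of sites and the site variance are not given, and the assay is standardised and read blind (Protocol 9.3). Variable bedside mixing would be a group-by-site effect, which an additive site term does not remove. This stands, and makes the efficiency gain conditional.
4. *Part of a three-group gain would not come from site.* In Part 1 with a 5% site share, t width divided by adjusted width is 1.006-1.012 with two groups plus site, and 1.022-1.026 when the third group is added. About half or more of the gain there is borrowed error variance, which assumes equal variances with and without CpG 1018. This stands, so the three-group fit should be optional.
5. *The objective 2 wording is conditional and reads most naturally as ANOVA first and t as fallback.* That is a fair reading, but it does not close the gap. The condition has no content until someone says when site can be used. The GMCs are also always raw, so it stays unclear which ratio the criterion refers to.

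**Conclusion.** The point holds as a gap in prespecification, with a modest efficiency loss beside it.

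For objective 2 the plan allows two estimators for a primary criterion judged on a point estimate, and fixes neither the choice nor the ratio to be read. The practical effect is small: the ratios usually agree within a few percent and disagree about the cut-off in roughly 0.4-5% of trials at true ratios of 2.0-2.5. It matters only when the result lies close to 2. The documents do not show that a method would be chosen for its result; they only fail to rule it out.

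For both ratios, an analysis without site gives intervals about 2-9% too wide if site explains 10-20% of the variance. If site explains nothing, there is no loss. These sizes rest on the assumed site counts and site shares; those for disagreement between the ratios also rest on the assumed SD.

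**What to change.** **SAP 8.6, Part 2 primary objective 2.** Replace the conditional wording with one primary model: ANOVA of log10 concentration on group and site. Add a rule, fixed before final unblinding, for pooling sites too small to inform the group contrast. State that the ratio from this model is the one compared with 2. Keep the raw GMCs as descriptive and the t result as descriptive or sensitivity.

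**SAP 8.6, Part 1.** Add site to the model for the ratios and their intervals. Fitting all three groups in one model is optional; if it is done, state the equal-variance assumption.

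**Cost.** SAP wording and one model statement, with no new data. With two groups of 20 and 6 sites, the error degrees of freedom fall from 38 to 40 − 2 − 5 = 33. If site has no effect, Part 1 intervals widen by at most about 2%, and objective 2 intervals are essentially unchanged.
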